6.8.3 Prohibited or Restricted Therapy

The following therapies are prohibited until study treatment has been permanently discontinued:

- Any investigational agent or investigational medical device.
- Oral anticoagulation with coumarin agents (e.g., warfarin), direct thrombin inhibitors (e.g., dabigatran), direct factor Xa inhibitor betrixaban, platelet inhibitors (e.g., clopidogrel), and chronic use of aspirin above low-dose levels for cardio protection per local applicable guidelines), until 4 weeks after cabozantinib has been permanently discontinued.

- Any nonprotocol systemic anticancer treatment (e.g., chemotherapy, immunotherapy, radionuclides, drugs or herbal products used specifically for the treatment of the cancer under investigation).

The following therapies should be avoided until study treatment has been permanently discontinued or until otherwise specified:

- Local anticancer treatment including palliative radiation, ablation, embolization, or surgery with impact on tumor lesions should not be performed on the RECIST v1.1 measurable lesions. Initiation of local anticancer therapy (e.g., palliative radiation) will be considered as progression of disease.
- Erythropoietic stimulating agents (e.g., epoetin alfa and darbepoetin alfa) should not be used based on a report of increased risk of tumor recurrence/progression associated with erythropoietin.
- Concomitant medications that are known to prolong the QTc interval should be avoided in subjects who receive cabozantinib until they have permanently discontinued study treatment (refer to <http://www.qtdrugs.org> for a list of drugs which have the potential to prolong the QTc interval).
- Chronic co-administration of cabozantinib with strong inducers of the CYP3A4 family (e.g., phenytoin, carbamazepine, rifampin, rifabutin, rifapentine, phenobarbital, and St. John's Wort) may significantly decrease cabozantinib concentrations and should be avoided. Selection of alternate concomitant medications with no or minimal CYP3A4 enzyme induction potential is recommended.
- Caution must be used when discontinuing treatment with a strong CYP3A4 inducer in a subject who has been concurrently receiving a stable dose of cabozantinib, as this could significantly increase the exposure to cabozantinib.

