6.9 Duration of Therapy

Subjects enrolled after Amendment 7 (version date 08NOV2021) will remain on study treatment for up to 12 months. After consultation with PI, subjects enrolled prior to Amendment 7 (version date 08NOV2021) who have demonstrated a response to study treatment may continue beyond 12 months of treatment, if there is demonstrated continued clinical benefit.

Study treatment may continue beyond initial radiographic or clinical disease progression for up to 12 months as long as the patient is deriving clinical benefit from the treatment, as assessed by the investigator.

Subjects must be withdrawn from the study treatment for the following reasons:

- Subject withdraws consent from the study treatment and/or study procedures. A subject must be removed from the trial at his/her own request or at the request of his/her legally acceptable representative. At any time during the trial and without giving reasons, a subject may decline to participate further. The subject will not suffer any disadvantage as a result.
- Radiographic disease progression by RECIST v1.1 (progression must be confirmed with follow up scan no less than 4 weeks and no more than 8 weeks after the first scan shows disease progression). Study treatment may continue beyond initial radiographic disease progression as long as the patient is deriving clinical benefit from the treatment, as assessed by the investigator.
- Progressive disease (PD), without clinical benefit, as determined by the investigator.
- Specific conditions described in the Management of Adverse Events Section 7.
- An AE or intercurrent illness that in the opinion of the investigator warrants the subject's withdrawal from study treatment.
- Subject is lost to follow-up.
- Necessity for treatment with other treatment prohibited by protocol.
- Sexually active subjects who refuse to use medically accepted barrier methods of contraception (e.g., male condom, female condom) during the course of the study and for 120 days after discontinuation of study treatment.
- Women who become pregnant or are breastfeeding.
- If the subject does not recover from his or her toxicities to tolerable Grade ≤ 2 within 6 weeks, the subject will have study treatment discontinued unless there is unequivocal evidence that the subject is benefitting. In this situation, a subject may be able to restart therapy with a dose reduction upon resolution of the toxicity.

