7.1 Dose Modifications and Guidelines for Adverse Event Management for Cabozantinib

Subjects will be monitored for AEs from the start of treatment through 30 days after the date of the last dose of cabozantinib treatment. Subjects will be instructed to notify their physician immediately at the onset of any AE. Causality assessment of AEs will be determined by the investigator. AE severity will be graded by the investigator in accordance with CTCAE v.5.0. The following should be taken into consideration in decisions regarding dose modifications (reductions or interruption):

- As a general approach, all AEs should be managed with supportive care at the earliest signs of toxicity considered related to the study treatment. Should this be ineffective, dose interruptions and/or reductions should be considered to prevent worsening of toxicity.
- The assigned starting dose for cabozantinib is 40 mg/day. Dose reductions are permitted per PI discretion (see Table 7.1). Dose re-escalation level (See 7.2) of cabozantinib is permitted.
- Dose interruptions and/or reductions should be implemented for unacceptable toxicity. Doses may be modified at any time while on study.
- Interruption of cabozantinib treatment for AEs may occur at any time per investigator discretion. If treatment is interrupted due to AEs for more than 6 weeks, all study treatment should be discontinued unless there is unequivocal evidence that the subject is benefitting. In this situation, a subject may be able to restart therapy with a dose reduction upon resolution of the toxicity.

- Dose interruptions for reason(s) other than related AEs (e.g., surgical procedures) can be longer than 6 weeks per the discretion of the investigator.

Table 7.1

Assigned dose	Dose Level Reduction
40-mg cabozantinib oral, qd	20-mg cabozantinib oral, qd.
20-mg cabozantinib oral, qd	20-mg cabozantinib oral, qad

Table 7.2

Assigned dose	Dose Level Escalation
20-mg cabozantinib, oral qad	20-mg cabozantinib, oral qd
20-mg cabozantinib, oral qd	40-mg cabozantinib, oral qd

Table 7.3: Dose Modifications of Cabozantinib for Treatment-Related AEs

CTCAE v.5.0 Grade	Recommended Guidelines for Management ^a
Grade 1 AEs	Add supportive care as indicated. Continue cabozantinib treatment at the current dose level if AE is manageable and tolerable.
Grade 2 AEs that are tolerable and are easily managed	Continue cabozantinib treatment at the current dose level with supportive care.

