Pembrolizumab may be interrupted for situations other than treatment-related AEs such as medical / surgical events or logistical reasons not related to study therapy. Subjects should be placed back on study therapy within 3 weeks of the scheduled interruption, unless otherwise discussed with the study sponsor (principal investigator). The reason for interruption should be documented in the patient's study record. Patients with a planned interruption may continue on the study with monotherapy of the other agent. Patients may also continue on the study with a planned permanent discontinuation of one of the study medications.

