9. Coagulation labs to be collected: PT/INR, APTT. Coagulation panel will only be required at EOT if patients are on active anticoagulant therapy and require monitoring.
10. Free T4, Free T3 and TSH must be performed at baseline and at least every 4th cycle during treatment
11. Pregnancy test (serum or urine- if urine is positive it must be confirmed with serum test) must be done at screening for all women of childbearing potential and every even cycle (2,4,6 ...etc.) during treatment (must be completed within 72hr prior to study enrollment)
12. ECG should be collected at screening (see section 9 for QTcF eligibility details at screening) and at every 4th cycle.
13. CT scans of chest, abdomen and pelvis will be repeated every 4th cycle during treatment within 1 week prior to the corresponding cycle (e.g., prior to cycle 5, 9, 13... etc.). However, if the study treatment is delayed, scans can be delayed to correspond to the treatment schedule, and this will not be a deviation. CT scans will be done at the end of treatment visit only if patient has come off for reasons other than progression. Use of contrast according to institutional practice is recommended but not required.
14. Bone Scans if clinically indicated for evaluation of bone metastatic disease
15. For participants who opt in to the optional tissue collection, tissue may be collected at pre-screening from an urothelial carcinoma diagnostic procedure (soft tissue biopsy or TURBT) or during screening from a soft tissue biopsy (only for patients who do not sign the pre-screening ICF). Subjects are also offered the option of a fresh soft-tissue biopsy or TURBT again prior to treatment at cycle 4 or after. See Section 14 for details.
16. For participants who opt in to the optional blood collection, blood may be collected on C1D1, C2D1, C4D1, C7D1, C13D1, and at end of treatment. See Section 14 for details.
17. For participants who opt in to the optional stool collection, stool may be collected and stool questionnaire administered within 3 days prior to treatment on C1D1, C2D1, C4D1, C7D1, C13D1, and at end of treatment. See Section 14 for details.
18. Cabozantinib at dose specified in dose escalation and specified in section 6.2. Subjects will complete dosing diary for each cycle (Appendix I)
19. Pembrolizumab 200 mg IV q3weeks
20. End of treatment visit should occur within 28 (± 14) days after subject completes study treatment

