10 CRITERIA FOR EVALUATION AND ENDPOINT

10.1 Efficacy

The primary objective is ORR with a secondary objective of PFS6. Evaluable subjects will be all patients who complete at least one set of disease assessment scans after starting protocol treatment. Patients who discontinue therapy due to clinical progression will also be considered evaluable even if they do not have a set of disease assessment scans.

Patients who discontinue treatment prior to one disease assessment evaluation will be deemed unevaluable and need to be replaced except if the patient was determined to have clinical progression as the reason for discontinuation of therapy. Disease assessments will be measured by CT or MRI scan. All evaluations and treatment decisions will be based on RECIST v1.1 criteria.^{28, 29} The iRECIST criteria³⁰ will be used as an exploratory measurement of efficacy which may be performed retrospectively.

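### On-treatment CT may slip with treatment delays without limit; a cumulative delay of more than about 2 to 3 weeks moves the second scan past 6 months and can modestly raise PFS6

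*Combined protocol and SAP*

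**What the plan says.** Footnote 13 of the Study Calendar places on-treatment CT at every fourth cycle, in the week before cycles 5, 9, 13 and so on, with 3-week cycles. It then says that "if the study treatment is delayed, scans can be delayed to correspond to the treatment schedule, and this will not be a deviation". Section 9.3 repeats this. Neither place sets a maximum scan delay or a calendar anchor.

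The only limits are on treatment holds, and each has a way round it:

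- **Unresolved toxicity (Section 6.9).** If toxicity has not recovered "within 6 weeks, the subject will have study treatment discontinued unless there is unequivocal evidence that the subject is benefitting".
- **Adverse-event holds (Section 7.1).** "If treatment is interrupted due to AEs for more than 6 weeks, all study treatment should be discontinued unless there is unequivocal evidence" of benefit.
- **Other cabozantinib holds (Section 7.1).** "Dose interruptions for reason(s) other than related AEs (e.g., surgical procedures) can be longer than 6 weeks per the discretion of the investigator".
- **Pembrolizumab interruptions not due to treatment-related events (Section 7.2).** "Subjects should be placed back on study therapy within 3 weeks of the scheduled interruption, unless otherwise discussed with the study sponsor".

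None of these limits is cumulative and none mentions scans. By contrast, patients who are off therapy without progression are imaged on a calendar rule, every 12 (± 1) weeks (footnote 21).

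PFS at 6 months is the first secondary objective (Section 1.2.1). Section 11.2 analyses PFS by Kaplan-Meier. The documents give no rule for the date of a progression event, no rule for late scans and no interval-censored analysis.

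**The concern.** Under this rule, the date on which progression is detected depends partly on how much treatment was delayed. The second scan is the last one due before 6 months. If it slips past the landmark, a patient who progressed after scan 1 counts as progression-free at 6 months unless something else reveals the progression first.

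The trial has one arm, and the hypothesis at the end of Section 2 refers to historic PFS benchmarks. With no concurrent control the bias does not cancel, and the Kaplan-Meier confidence interval does not reflect it.

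**Working it through.** **The plan's own figures.** The plan states no figure for PFS6. Its ORR figures reproduce: the one-sided 95% Clopper-Pearson lower bound is 33.8% for 17/35 and 31.2% for 16/35, so 17 is the smallest count that excludes 32%. Also 35/0.9 = 38.9, rounded up to 39. The scan rule touches neither.

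**Timing.** Time is counted from cycle 1 day 1 (assumed origin).

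- Cycle 9 day 1 is day 8 × 21 = 168. The scan is due in the preceding week, days 161-168 (weeks 23-24).
- Six months = 6 × 365.25/12 = 182.6 days = 26.09 weeks.
- Delay needed to pass the landmark: 26.09 − 24 = 2.09 weeks to 26.09 − 23 = 3.09 weeks.
- Other readings of 6 months: 26 weeks gives 2.0-3.0 weeks; 180 days gives 1.7-2.7 weeks.

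One permitted 6-week adverse-event hold that delays the cycle is enough.

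**Model.** PFS is taken as exponential, S(t) = exp(−ln 2 × t / median), with medians 4.8 and 7.6 months (the chemotherapy figures in Section 11.1). Progression is dated to the scan that finds it, and scan 1 is 84 days before scan 2.

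- On time: observed PFS6 = S(scan 2).
- Delayed, but still before day 182.6: S(delayed scan 2).
- Delayed past day 182.6: S(scan 1) if the delay came after scan 1, or S(scan 1 + delay) if it came before.

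| Median | S(wk 11) | S(12) | S(15) | S(16) | S(23) | S(24) | S(26.09) |
|---|---|---|---|---|---|---|---|
| 4.8 mo | 0.694 | 0.671 | 0.608 | 0.588 | 0.466 | 0.451 | 0.420 |
| 7.6 mo | 0.794 | 0.777 | 0.730 | 0.715 | 0.617 | 0.604 | 0.579 |

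**Shift per delayed patient, in percentage points** (from unrounded values, over scan days 161-168):

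| Cumulative delay | Median 4.8 mo | Median 7.6 mo |
|---|---|---|
| 1 week | −1.5 | −1.3 |
| 2 weeks | −2.9 to −3.0 | −2.5 |
| 3 weeks, scan due day 161 (moves to day 182) | −4.4 | −3.8 |
| 3 weeks, scan due days 162-168 | +15.7 to +22.7 | +12.6 to +17.6 |
| 4 weeks, after scan 1 | +22.1 to +22.8 | +17.3 to +17.7 |
| 4 weeks, before scan 1 | +13.7 to +14.2 | +11.0 to +11.3 |

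For example, at median 4.8 months with a scan due on day 161 and a 4-week delay after scan 1: 0.694 − 0.466 = 0.228.

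**Shift in the trial's PFS6.** The documents give no frequency of delay, so I assume that 10-25% of patients have a cumulative 4-week delay by cycle 9.

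- 10%: 0.10 × 11.0 to 0.10 × 22.8 = 1.1 to 2.3 points.
- 25%: 0.25 × 11.0 to 0.25 × 22.8 = 2.8 to 5.7 points.
- Overall 1.1-5.7 points, or 0.4-2.0 patients of 35.
- If half of these events are found between scans: 0.6-2.9 points, or 0.2-1.0 patients of 35.

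**Scale.** One patient of 35 is 2.9 points. The standard error is √(0.42 × 0.58/35) = 8.3 points.

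**After the fix.** With scan 2 held to weeks 23-25 it always precedes week 26.09. Dating progression to scans still overstates PFS6 by S(25) − S(26.09) to S(23) − S(26.09): 1.5-4.5 points at median 4.8 months and 1.3-3.9 at 7.6 months.

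**The case against.** The case for leaving the rule alone is reasonable, and much of it stands.

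- **Size.** PFS6 is secondary, has no target or decision rule, and the shift is below one standard error. This stands. However, the shift is systematic, and the confidence interval does not cover it.
- **Assumed inputs and direction.** The share delayed and the 4-week length are assumptions. Delays of 1-2 weeks lower PFS6 slightly, and 3 weeks can go either way. This stands: the net effect over a realistic mix of delays is not established.
- **Holding one agent.** Section 7.2 says "Patients with a planned interruption may continue on the study with monotherapy of the other agent", so a cabozantinib hold need not move the cycle or the scan. This stands, although the plan does not say whether holding one drug counts as delayed treatment for footnote 13.
- **Events found between scans.** Section 6.8.3 says "Initiation of local anticancer therapy (e.g., palliative radiation) will be considered as progression of disease". Section 10.1 says "Patients who discontinue therapy due to clinical progression will also be considered evaluable", so progression can be recognised without a scan. Responders have a confirmatory scan 4 to 6 weeks later (Section 10.1.1), and deaths need no scan. The upper figure of 5.7 points assumes that none of this happens, so the halved range is more credible.
- **Imaging after discontinuation.** Patients who stop without progression have an end-of-treatment CT and then calendar-based imaging (Sections 9.4 and 9.5). This limits the problem for holds that end in discontinuation, but not for patients who resume.
- **The remedy leaves 1.3-4.5 points.** True, and that can match or exceed the bias removed. The residual comes from 12-week scan dating and does not depend on treatment delays. The jump of 11-23 points in a patient delayed by 4 weeks does, and the anchored schedule removes it. The residual is the reason for the interval-censored analysis.

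**Conclusion.** The concern holds as a modest design weakness. The scan rule has no cap, the hold limits do not bound cumulative delay, and the analysis has no provision for late scans. A cumulative cycle delay of more than 2.1-3.1 weeks takes scan 2 past 6 months. The illustrative effect is a rise in PFS6 of 1.1-5.7 points, or 0.6-2.9 points if half of the events surface between scans. The primary ORR threshold of 17/35 is not affected.

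This rests on exponential PFS, an origin at cycle 1 day 1, 6 months read as 182.6 days, a 4-week delay in 10-25% of patients, and the scan timing in footnote 13. Section 10.1.1 refers to a 9-week interval in the schedule of events, which does not match every fourth 3-week cycle and should be reconciled with it. The change is worth making because it costs little, not because the bias is large.

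**What to change.** 1. **Footnote 13 and Section 9.3.** State that CT is done every 12 weeks (± 1 week) counted from cycle 1 day 1, regardless of dose holds or cycle delays. Delete the sentence that lets scans move with treatment. Scan 2 then falls in weeks 23-25, before week 26.1. The interval is the one already used off treatment.
2. **Section 11.2.** State that progression is dated to the scan that first shows it, and add an interval-censored sensitivity analysis of PFS6 based on actual scan dates.

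**Cost.** Protocol wording and one extra analysis, with no change in the 12-week interval. Some scans will no longer coincide with an infusion visit. Patients enrolled before the change will have followed the old rule, so two schedules are mixed within about 35 evaluable patients; for the earlier patients only the sensitivity analysis helps. If the sponsor prefers not to change the schedule during the study, the second item is still useful on its own.

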9 STUDY PROCEDURES

9.1 Pre-Screening

Pre-screening informed consent

Pre-screening eligibility review

Optional tissue collection (at the time of the standard of care urothelial carcinoma diagnostic procedure) within 4 weeks of study registration

9.2 Screening

Informed Consent

Physical exam

Vital Signs (incl. height/weight)

Review of medical history/baseline symptoms/smoking history/concomitant medications

ECOG Performance status

Labs:

- CBC w/diff
- CMP – Albumin, Alkaline Phosphatase, Aspartate Aminotransferase, Alanine Aminotransferase, Total Bilirubin, Calcium, Carbon Dioxide, Creatinine, Chloride, Glucose, Potassium, Protein, Sodium, Urea Nitrogen, phosphorous and magnesium.
- Additional Labs: LDH, Lipase, Lipid Panel, Gamma Glutamyl Transferase, B-type Natriuretic peptide
- Coagulation – PT/INR, APTT
- Thyroid function – TSH, Free T4, Free T3
- Serum pregnancy test (for women of childbearing potential)
- Urinalysis including urine protein creatinine ratio
- Viral Hepatitis Screening (if clinically indicated)

ECG: If a single ECG shows a QTcF with an absolute value > 500 ms, two additional ECGs at intervals of approximately 3 min must be performed within 30 min after the initial ECG, and the average of these three consecutive results for QTcF will be used to determine eligibility.

CT scans of chest/abdomen/pelvis

Bone Scans if clinically indicated

Optional Tissue Collection for correlatives see section 14

9.3 On-Treatment Evaluations

Physical Exam – **at each cycle**

ECOG Performance Status – at each cycle

Vital Signs (Incl. weight) – at each cycle

Labs: (do not need to be repeated if screening labs performed within 14 days of C1D1)

- CBC w/diff – **at each cycle**
- CMP – Albumin, Alkaline Phosphatase, Aspartate Aminotransferase, Alanine Aminotransferase, Total Bilirubin, Calcium, Carbon Dioxide, Creatinine, Chloride, Glucose, Potassium, Protein, Sodium, Urea Nitrogen, phosphorous and magnesium. – **at each cycle**
- Additional Labs: LDH, Lipase, Lipid Panel, Gamma Glutamyl Transferase, N-type Natriuretic peptide – **at every fourth cycle (4, 8, 12...)**
- Coagulation – PT/INR, APTT – at every fourth cycle (4, 8, 12...)
- Thyroid function – TSH, Free T4, Free T3 – at every fourth cycle (4, 8, 12...)
- Serum pregnancy test (for women of childbearing potential) at every even cycle **(2, 4, 6...)**
- Urinalysis including urine protein creatinine ratio – **at every cycle**

ECG – at every fourth cycle (4, 8, 12...)

Safety assessment - Monitoring and recording all adverse events and serious adverse events using the CTCAE version 5.0 – **at each cycle**

Review of concomitant medications – **at each cycle**

CT scans of the chest/abdomen/pelvis and response assessment by RECIST v1.1 to be **repeated every 4th cycle**. However, if the study treatment is delayed, scans can be delayed to correspond to the treatment schedule, and this will not be a deviation.

Bone Scans if clinically indicated

Optional Tissue Collection for correlates at **cycle 4**, or after, see section 14

Optional Blood and Stool Collection and administration of Stool Questionnaire for correlates – **at C1D1, C2D1, C4D1, C7D1, C13D1** see section 14

Treatment with 200mg pembrolizumab per section 6.3

Treatment with appropriate dose of cabozantinib – review of patient dosing diary per section 6.2

9.4 End of Treatment Assessments (completed 28 days ± 14 days after completion of treatment)

Physical exam

Vital Signs

Concomitant medication collection

ECOG Performance status

Labs:

- CBC w/diff
- CMP – Albumin, Alkaline Phosphatase, Aspartate Aminotransferase, Alanine Aminotransferase, Total Bilirubin, Calcium, Carbon Dioxide, Creatinine, Chloride, Glucose, Potassium, Protein, Sodium, Urea Nitrogen. Phosphorus and magnesium
- Additional Labs: LDH, Lipase, Lipid Panel, Gamma Glutamyl Transferase, B-type Natriuretic peptide
- Thyroid function – TSH, Free T4, Free T3
- PT/INR, aPTT if patients are on active anticoagulant therapy and require monitoring
- B-type Natriuretic peptide
- Urinalysis including urine protein creatinine ratio

Optional Blood and Stool Collection and administration of Stool Questionnaire for correlatives see section 14

Adverse event collection for 30 days

CT scans of the chest/abdomen/pelvis and response assessment by RECIST v1.1 to be performed at the end of treatment visit only if patient has come off for reasons other than progression

